4.9 Duration of study

The total duration of the study will be 20 weeks from the day of enrolment for participants enrolled in groups 1-2. The total duration of the study for participants enrolled in groups 3 and 4 will be 12 weeks from the day of enrolment. The total duration of the study for participants enrolled in group 5 will be 20 weeks from the day of enrolment

4.10 Definition of start and end of trial

The start of the trial is defined as the date of consent of the first participant. The end of the trial is the date of the last visit of the last participant.

5 Data analysis plan - Data description

5.1 Recruitment and patient progression

A CONSORT flow chart will be constructed – see Figure 1. This will include the number of eligible patients, number of patients agreeing to enter the trial, number of patients refusing, the number continuing through the trial, the number withdrawing, the number lost to follow-up and the numbers excluded/analysed.

^{**}Use clinical judgement when characterising bradycardia among some healthy participant populations, for example, conditioned athletes.

^{***}Only if symptomatic (e.g. dizzy/ light-headed)

Screened n=# Reasons for noneligibility: n (%) Eligible n=# Reasons for nonconsent: n (%) Consented n=# Enrolled (Vaccinated) n=# Reasons for withdrawal: n (%) Completed followup n=# Reasons for noncompliance: n (%) Analysed n=#

Figure 1 Template CONSORT diagram for HAV002 trial

5.2 Patient status

Status for all enrolled participants will be given according to the sample table below:

Table 5 Patient status

Participant	Date screened	Date consented	Date of enrolment/	Group number (* denotes the first patient for that group)	Completed trial (Y/N)	Withdrawal date	Reason for withdrawal
Patient 1							
Patient 28							

5.3 Baseline description of groups

Baseline descriptions of all enrolled participants (e.g. age, gender, ethnicity) will be given overall and by group, using means and standard deviation or numbers and proportions as appropriate.

5.4 Protocol deviations

Details of protocol deviations, such as visits outside of allowable window, missing procedures or procedures taken outside of visit will be given overall by group.

5.5 Loss to follow-up and other missing data

The proportions of participants missing each variable will be summarised at each time point.

The baseline characteristics of those missing follow up will be compared to those with complete follow up.

The reasons for withdrawal from the trial will be summarised.

5.6 Adverse event reporting

Local and systemic Adverse events (AE), adverse reactions (AR), serious adverse events (SAE) and serious adverse reactions (SAR) will be summarised overall by group.

6 Data analysis plan - analysis of endpoints

6.1 Analysis of primary endpoint

Determining the Maximum Tolerated Dose (MTD) for ChAdOx2 HAV will depend on the response of patients in Group 1 and 2. As stated in the Group Holding rules, if 2 or more participants in Group 2 experience Grade 3 SAR lasting more than 48 hours, then the previously tolerated dose will be recorded as the MTD. If 2 or more participants in Group 1 experience Grade 3 SAR lasting more than 48 hours, then the trial will be put on hold pending an internal safety review.

If less than 2 participants in Group 2 experience the outcome stated above, then participants in Group 3 and 4 will be subject to the same criteria for the two doses of MVA HAV. If 2 or more participants in Group 4 experience Grade 3 SAR lasting more than 48 hours, then the previously tolerated dose will be recorded as the MTD. If 2 or more participants in Group 3 experience Grade 3 SAR lasting more than 48 hours, then the trial will be put on hold pending an internal safety review.

Once the MTDs for ChAdOx2 HAV and MVA HAV is determined, then participants in Group 5 will be subject to these doses. If 2 or more participants in Group 5 experience Grade 3 SAR lasting more than 48 hours, then the trial will be put on hold pending an internal safety review.

The proportion of all individuals per group who experience Grade 3 SAR lasting more than 48 hours at the end of follow-up will be estimated with a 95% exact confidence interval. The number with expected and unexpected AEs and all SAEs will be presented alongside, according to the sample table below:

Table 6 Summary of adverse events by Group

Number experiencin experiencin g Grade 3 enrolled SAR lasting more than 48 hours Proportion experiencin g Grade 3 SAR lasting more than 48 hours (95% CI)	Number of expected local reactogenicit y signs and symptoms for 7 days following the	Number of expected systemic reactogenicit y signs and symptoms for 7 days following the	Number of unexpected adverse events for 28 days following the vaccination	Number of serious adverse events during the whole study duration
---	--	---	---	--

		vaccination	vaccination	
Group 1				
Group 5				

The median and range of values of safety laboratory measures will be plotted by group at baseline (vaccination visit) and 7 days post vaccination.

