3.2.3 Group holding rules

For safety reasons the first participant to receive a new vaccine dose will be vaccinated alone and we will wait 48 hours before vaccinating subsequent participants. Two further participants may be vaccinated 48 hours after the first, and then at least another 48 hours gap will be left before vaccinating the rest of the participants receiving that dose of vaccine.

If the first three 2.5×10^{10} vp doses are deemed safe (none of the first three participants experiences a Grade 3 severe adverse reaction lasting more than 48 hours), the first patient in the higher dose of 5×10^{10} vp will be vaccinated at the same time as the remaining 3 at the lower dose. Two further participants may be vaccinated at the higher dose, 48 hours after the first, and then at least another 48 hours gap will be left before vaccinating the rest of the participants at the 5×10^{10} vp dose.

If 2 or more participants in groups 1-2 experience Grade 3 severe adverse reactions lasting more than 48 hours at a given dose, then no further participants will be vaccinated at that dose or a higher dose and the previously tolerated dose will be recorded as the Maximum Tolerated Dose (MTD).

The group holding rules are as follows (groups 1-5)

Solicited local adverse events:

 If 2 vaccinations in a group are followed by the same Grade 3 solicited local adverse event beginning within 2 days after vaccination (day of vaccination and one subsequent day) and persisting at Grade 3 for >48 hrs.

Solicited systemic adverse events:

 If 2 vaccinations in a group are followed by the same Grade 3 solicited systemic adverse event beginning within 2 days after vaccination (day of vaccination and one subsequent day) and persisting at Grade 3 for >48 hrs.

Unsolicited adverse events:

 If 2 vaccinations in a group are followed by the same Grade 3 unsolicited adverse event beginning within 7 days after vaccination that is considered related to vaccination and persists at Grade 3 for >48 hrs.

• Laboratory adverse event:

- If 2 vaccinations in a group are followed by the same Grade 3 laboratory adverse event beginning within 7 days after vaccination and persists at Grade 3 for >72 hrs.
- A serious adverse event considered possibly, probably or definitely related to vaccination occurs
- Death occurs
- A life-threatening reaction occurs

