3.3.1 Secondary outcome measures

Immunogenicity

Measures of immunogenicity may include:

ELISPOT to enumerate IFN-γ producing T cells

Other exploratory immunology may be carried out in collaboration with other specialist laboratories. This would involve transfer of serum/plasma and/or peripheral blood mononuclear cells (PBMC), but samples would be anonymised. Participants will be consented for this.

Sampling of exploratory immunology responses

20ml of whole blood will be taken at baseline (D0) and days 28 and 56 (groups 1 and 2). For Group 5 10ml of whole blood will be taken at screening, with 30ml taken at baseline (D0) and days 56 and 112 and an additional 20ml on days 28 and 84 of the study for use in assays to measure immune responses of various types to the vaccine.

Assessment of clinical response

All participants will undergo an evaluation of Crohn's disease activity at screening and at day 56 for groups 1-4. Group 5 will undergo an evaluation of Crohn's disease activity at screening, on day 56 and again on day 112. For Group 5, endoscopic scoring by flexible sigmoidoscopy or colonoscopy will be undertaken by the CD-SES (simple endoscopic score) at screening and at day 112.

Exploratory immunology may be carried out in collaboration with other specialist laboratories. This would involve transfer of serum/plasma and/or peripheral blood mononuclear cells (PBMC), but samples would be anonymised. Participants will be consented for this.

4 Trial design

This is a phase Ib open-label dose escalation study to assess the safety, tolerability and immunogenicity of the candidate Mycobacterium avium subspecies

paratuberculosis (MAP) vaccine, ChAdOx2 HAV in patients with active Crohn's disease aged 18-50.

Participants will be enrolled and doses will be escalated according to a study plan which will run as outlined in section 8.4.2.2 of the protocol and summarized in the table below:

Table 1 Summary of dosing regimen

Group	Dose
1 (n=6)	ChAdOx2 HAV, 2.5x1010 vp
2 (n=6)	ChAdOx2 HAV, 5x1010 vp
3 (n=3)	MVA HAV, 5x107 pfu
4 (n=3)	MVA HAV, 2x10 ₈ pfu
5 (n=10)	Prime boost Regime (doses depended on
	the results from Groups 1-4)

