6.3 Statistical considerations

Time points

The primary outcome is measured across all follow-up time period (2 or more participants experiencing Grade 3 severe adverse reactions (SAR) lasting more than 48 hrs). Secondary outcomes are presented using descriptive statistics for baseline and follow-up timepoints. Data will be presented using descriptive statistics and no repeated measures analysis will be conducted.

Stratification and clustering

There will be no stratification or clustering

Missing baseline data

Individuals must have all baseline measurements as part of screening and as standard of care. This data will not be imputed for the primary analysis.

Missing outcome data

Individuals will be monitored for the entire followup duration and thus there will be no missing data for the primary outcome. If data is missing for the secondary or exploratory outcomes analysis will be carried out on a complete case basis with no imputation.

Method for handling multiple comparisons

Bonferroni adjustment for multiple comparisons will be used.

Method for handling non-compliance (per protocol/CACE analyses)
Since this is a single arm trial CACE analysis is not possible

Model assumption checks

Only descriptive statistics will be presented for all outcomes and thus no model assumption checks are needed. As the sample size is small, medians and IQRs will be presented instead of means and standard deviations.

Sensitivity analyses

No sensitivity analyses are planned

Planned subgroup analyses

No subgroup analyses are planned

Interim analysis

Interim safety reviews are planned after vaccinating the first participants in all groups, and prior to moving up a dose. The safety reviews are summarized in the table below, and described in more detail in section 4.4 to 4.7

Safety reviews

Table 7 Planned interim safety reviews

Interim safety	When
review	
1	After vaccination of the first participant in
	Group 1
2	After vaccination of the participant 2 and 3
	in Group 1, and prior to vaccinating
	participants 4-6 in Group 1 and participant
	1 in Group 2
3	After vaccination of the first participant in
	Group 2
4	After vaccination of the first participant in
	Group 3
5	After vaccination of the participant 2 and 3
	in Group 3, and prior to vaccinating the first
	participant in Group 4
6	After vaccination of the participant 2 and 3
	in Group 4, and prior to vaccinating the first

	participant in Group 5
--	------------------------

7 Software

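### The primary event depends on an unblinded causality judgement, and no all-cause Grade 3 count is planned beside it, so a reader could not see how far attribution moved the rate

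*SAP*

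**What the plan says.** The one proportion that receives an interval, an exact 95% one, is described in SAP 6.1: "The proportion of all individuals per group who experience Grade 3 SAR lasting more than 48 hours at the end of follow-up". Section 6.3 gives the primary outcome as "2 or more participants experiencing Grade 3 severe adverse reactions (SAR) lasting more than 48 hrs", measured over all follow-up. Sections 3.2.3 and 6.1 use the threshold of 2 to fix the MTD.

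Section 5.6 keeps events and reactions apart and expands the abbreviation differently: "Local and systemic Adverse events (AE), adverse reactions (AR), serious adverse events (SAE) and serious adverse reactions (SAR) will be summarised overall by group".

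On what accompanies the primary rate, 6.1 says: "The number with expected and unexpected AEs and all SAEs will be presented alongside". The Table 6 columns are expected local and systemic reactogenicity to 7 days, unexpected adverse events to 28 days, and serious adverse events throughout. None is divided by grade or duration.

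The holding rules in 3.2.3 are worded differently from the MTD rule. One begins "If 2 vaccinations in a group are followed by the same Grade 3 solicited systemic adverse event" and sets no relatedness condition. The solicited local and laboratory rules set none either; the unsolicited rule does.

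On design, section 4 says: "This is a phase Ib open-label dose escalation study". On sensitivity analysis, 6.3 says: "No sensitivity analyses are planned".

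**The concern.** A reaction, as distinct from an event, has been judged to be caused by the vaccine. Here everyone making that judgement knows the participant was vaccinated, there is no control group to show the background rate, and the participants have an active disease that may itself produce severe symptoms. Section 3.2.3 has the internal safety review consider other possible causes, so the plan itself expects competing explanations.

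A Grade 3 event lasting more than 48 hours that is put down to Crohn's disease leaves the primary count. One caused by Crohn's disease but put down to the vaccine enters it. Neither movement would be visible in the planned tables. In groups of 3 or 6 with a threshold of 2, a single such decision can determine whether the criterion is met and can halve the reported proportion.

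**Working it through.** **Inputs.** Group sizes 6, 6, 3, 3 and 10 (Table 1); threshold 2 or more participants (3.2.3, 6.1); exact 95% interval (6.1). The sizes add up: 6 + 6 + 3 + 3 + 10 = 28, the maximum in the Synopsis. The SAP states no expected event rate or operating characteristic, so there is no other figure to reproduce. All rates and attribution fractions below are assumptions.

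**1. One attribution and the reported rate.** The exact (Clopper-Pearson) limits for x of n are the 0.025 quantile of Beta(x, n−x+1) and the 0.975 quantile of Beta(x+1, n−x).

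| Group size | Both events judged related | One judged unrelated |
|---|---|---|
| 3 | 2/3 = 66.7% (9.4% to 99.2%) | 1/3 = 33.3% (0.8% to 90.6%) |
| 6 | 2/6 = 33.3% (4.3% to 77.7%) | 1/6 = 16.7% (0.4% to 64.1%) |
| 10 | 2/10 = 20.0% (2.5% to 55.6%) | 1/10 = 10.0% (0.3% to 44.5%) |

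In each row the left-hand count meets the threshold and the right-hand count does not.

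**2. Under-attribution.** Let p be the rate of vaccine-caused Grade 3 events lasting more than 48 hours, s the share judged related, and q = p × s. Treating participants as independent, P(2 or more) = 1 − (1−q)^n − nq(1−q)^(n−1).

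For n = 6, p = 1/3, s = 1: 1 − 0.088 − 0.263 = 0.649.

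| n | p | s = 1 | s = 0.7 | s = 0.5 |
|---|---|---|---|---|
| 6 | 1/3 | 0.649 | 0.426 | 0.263 |
| 6 | 0.20 | 0.345 | 0.200 | 0.114 |

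**3. Over-attribution.** Let the vaccine-caused rate be v = 0.10, the background rate of similar events b = 0.20, and the share of background events judged related f = 0.5. Then q = 1 − (1−v)(1−bf) = 1 − 0.9 × 0.9 = 0.19. For n = 6 the chance of 2 or more rises from 0.114 (f = 0) to 0.320.

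**4. What the planned outputs would show.** Take a non-serious Grade 3 event lasting more than 48 hours and judged unrelated.

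- With onset within the Table 6 windows, it is one item in a count of events of all grades.
- With onset after day 28, it is in no Table 6 column, although the primary outcome runs over all follow-up and the schedules ascertain adverse events to day 140 (Groups 1, 2 and 5) or day 84 (Groups 3 and 4). Section 5.6 would include it, ungraded.

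**5. What an all-cause count adds.** Participants with a related event are a subset of those with any such event, so the related count cannot exceed the all-cause count. The gap between the two is the most that under-attribution could have removed. The all-cause count does not measure over-attribution.

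**The case against.** Basing the MTD on reactions is a legitimate choice, and section 6.1 misstates nothing on this point. Who judges causality, and by what definition, is commonly left to the protocol, which is not at hand. Both statements stand; the point concerns what the SAP's own tables would reveal, not the choice of rule.

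Four stronger readings are tempting, and the SAP does not support them.

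- *The rate is biased low.* The direction is not established. Step 3 shows the opposite error raising the chance of meeting the threshold. Injection-site events could hardly be put down to Crohn's disease, so applying one attribution fraction to every event, as step 2 does, probably overstates the effect. The SAP does not list the solicited systemic symptoms, so their overlap with Crohn's symptoms is inferred.
- *Attribution alone decides which dose goes into Group 5.* It does not. The solicited and laboratory holding rules need no relatedness. Under 4.5 the safety reviews assess the profile and severity of adverse events, not only reactions, and under 4.7 the chief investigator and the committee decide on starting Group 5. These safeguards are incomplete: the rules named need the same event after two vaccinations and within set onset windows. They also do nothing for the reported rate. In Group 5 itself, reaching the threshold leads to a hold, not to a lower MTD.
- *The gap is the same whatever SAR means.* It is not. If SAR means serious adverse reaction, as in 5.6, every SAR is also an SAE, and Table 6 already shows SAEs over the whole study without a causality limit. That bound is only approximate, because the column counts events without grade or duration. Sections 3.2.3 and 6.3 support the *severe* reading, under which the gap is real.
- *The participants are untreated.* The SAP excludes immunosuppressive and immunomodulatory treatment, not all treatment, and describes the disease as mild to moderately active.

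**Conclusion.** The point holds as a reporting gap under the *severe* reading of SAR. The primary proportion and the MTD count rest on an unblinded causality judgement, and no planned output shows what they would be without it. One attribution moves 2/6 (4% to 78%) to 1/6 (0.4% to 64%) and across the threshold. Those intervals overlap almost entirely, so the consequence lies in whether the criterion is met and in the point estimate, not in any precise inference about the rate.

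Under assumed rates of 20% to 33% and 30% to 50% of events judged unrelated, the chance of reaching 2 of 6 falls from between 0.345 and 0.649 to between 0.114 and 0.426. Under the assumed over-attribution it rises from 0.114 to 0.320. These figures show sensitivity; they do not predict a direction. The effect on dosing decisions is tempered by the holding rules and the committee reviews. This is a worthwhile, inexpensive improvement and does not show that the primary analysis is wrong.

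**What to change.** - In 6.1 and Table 6, beside the related count, add the number and proportion (exact 95% CI) of participants per group with any Grade 3 adverse event lasting more than 48 hours, irrespective of causality, over the same follow-up as the primary outcome.
- List each such event judged unrelated, with group, onset, duration and the cause assigned.
- In 6.3, replace the statement that no sensitivity analysis is planned with this one.
- Reconcile the meaning of SAR between 5.6 (serious) and 6.3 (severe).

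The MTD rule is left unchanged. The cost is SAP wording, one further entry in Table 6 and a listing, drawn from severity grading (4.8) and adverse event ascertainment (schedules of procedures) that are already planned. The downside is that the all-cause count will include true Crohn's events. It should be labelled an upper bound shown beside the primary count, not a replacement for it.

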3.2.2 Primary outcome measures

To define the Maximum Tolerated Dose (MTD) of ChAdOx2 HAV and MVA HAV in patients with active Crohn's disease on no current immunosuppressive therapy when administered alone and in a prime-boost regimen. The definition of MTD is defined as per the Group Holding Rules in section 3.2.3.

The following parameters will be used to assess response and safety for all study groups:

- Occurrence of local reactogenicity signs and symptoms for 7 days following the vaccination
- Occurrence of systemic reactogenicity signs and symptoms for 7 days following the vaccination
- Occurrence of adverse events for 28 days following the vaccination
- Change from baseline for safety laboratory measures
- Occurrence of serious adverse events during the whole study duration

Participants in groups 1-2 will undergo clinical follow up for a further 20 weeks following completion of the vaccination regimen. SAEs will be collected throughout the study.

Participants in groups 3-4 will undergo clinical follow-up for a further 12 weeks following completion of the vaccination regimen. SAEs will be collected throughout the study. Participants in group 5 will undergo clinical follow-up for a further 20 weeks following completion of the vaccination regimen. The duration of follow up reflects the desire to obtain sufficient safety data with the first use of ChAdOx2 HAV, MVA HAV and a prime-boost regimen with ChAdOx2 HAV-MVA HAV in humans with Crohn's Disease. Considering the pre-existing safety data on several other MVA based constructs, participants receiving MVA HAV will be followed by a shorter period.

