8 B) SCHEDULE OF ASSESSMENTS AND MEASURES

Table 4. Schedule of procedures for study for groups 1 and 2

Attendance No.	1	2	3	4	5	6	7	8
Visit	Screening	Vaccination Visit	Follow Up 1	Follow Up 2	Follow Up 3	Follow Up 4	Follow Up 5	Follow Up 6
Timeline (days)**	<30	0	Day 2	Week 1 (Day 7)	Week 2 (Day 14)	Week 4 (Day 28)	Week 8 (Day 56)	Week 20 (Day 140)
Time window (days)			± 1	± 1	± 2	± 7	± 7	± 7
Informed consent	х							
Review contraindications, concomitant medication, inclusion and exclusion criteria	x	х						
Vaccination		х						
Vital signs ^	х	х	х	х	х	х	х	
Ascertainment of adverse events ***		х	х	х	х	х	х	х
Diary cards provided		х						
Diary cards collected						х		
Telephone Contact								х
Crohn's disease activity assessments	х						х	
Medical history	х							

Physical examination	х	х	(x)	(x)	(x)	(x)	(x)	
Biochemistry, Haematology (ml)	8	8	8	8		8		
Exploratory immunology (ml)		20				20	20	
Exploratory microbiology (ml)		10				10	10	
Urinalysis	х							
Urinary β-HCG (women only)	х	х						
HLA typing (ml)		4						
HBsAg, HCV Ab, HIV serology (ml)	5							
SARS-CoV-2 swab test	х							
Total blood volume per visit (ml)	13	32	8	8	0	28	20	0

(X) = if considered necessary $^* = Vital$ signs includes pulse, blood pressure and temperature; \$ = Biochemistry will include Sodium, Potassium, Urea, Creatinine, Albumin and Liver function tests. £ = Exploratory immunology includes ex vivo ELISPOT responses to interferon gamma ** Timeline is approximate only. Exact timings of visits relate to the day on enrolment, i.e., each visit must occur at indicated number of days after enrolment ± time window. *** Redness and swelling will be assessed by the clinical team following vaccination at days 0, 2 and 7.

Table 5. Schedule of procedures for study groups 3 and 4

Attendance No.	1	2	3	4	5	6	7	8
Viola	Canaanina	Vaccination	Follow	Follow	Follow	Follow	Follow	Follow
Visit	Screening	Visit	Up 1	Up 2	Up 3	Up 4	Up 5	Up 6
Timediae (dove)**	<30	0	Day 2	Week 1	Week 2	Week 4	Week 8	Week 12
Timeline (days)**				(Day 7)	(Day 14)	(Day 28)	(Day 56)	(Day 84)

Time window (days)			± 1	± 1	± 2	± 7	± 7	± 7
Informed consent	х							
Review contraindications, concomitant medication, inclusion and exclusion criteria	х	х						
Vaccination		х						
Vital signs ^	х	х	х	х	х	х	х	
Ascertainment of adverse events ***		х	х	х	х	х	х	х
Diary cards provided		х						
Diary cards collected						х		
Telephone Contact								х
Crohn's disease activity assessments	х						х	
Medical history	х							

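### Section 6.1 does not report laboratory change from baseline, a listed primary safety measure, and its Table 6 merges Group 5's prime and boost events in one row

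*SAP*

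**What the plan says.** Section 3.2.2 lists the parameters for judging safety in every group. One is "Change from baseline for safety laboratory measures". Another is "Occurrence of adverse events for 28 days following the vaccination", with no restriction to unexpected events. Reactogenicity has its own shorter window, for example "Occurrence of local reactogenicity signs and symptoms for 7 days following the vaccination".

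Section 6.1 then names the outputs. For laboratory measures: "The median and range of values of safety laboratory measures will be plotted by group at baseline (vaccination visit) and 7 days post vaccination". For adverse events: "The number with expected and unexpected AEs and all SAEs will be presented alongside, according to the sample table below". That shell, "Table 6 Summary of adverse events by Group", has one row per group and a column for the number enrolled. Its other columns cover Grade 3 reactions lasting beyond 48 hours, expected local and systemic reactogenicity (7 days), unexpected adverse events (28 days) and SAEs (whole study). The headings refer to a single vaccination.

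Section 5.6 adds a general summary by group of adverse events, adverse reactions and their serious counterparts, with no time window. Section 4.4 gives Group 5 ChAdOx2 HAV on day 0 and MVA HAV on day 56. The schedules in section 8 show when safety bloods are drawn.

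**The concern.** The listed measures and the planned outputs do not match in three places.

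- **Laboratory change.** A primary parameter is defined as change, but the output shows group values at two times. With 3 to 10 people per group, the useful information is what happened to each person, and the plot removes it.
- **Group 5.** Two different vaccines, eight weeks apart, share one row. A reader of the table cannot tell which dose the events followed, and someone who never received the boost is still counted as if exposed to it.
- **28-day events.** The primary table counts a narrower set of events than 3.2.2 lists.

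At stake is whether the trial report answers the primary safety questions as written, or leaves the analyst to choose further displays after seeing the data.

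**Working it through.** The only stated total is the maximum sample size, and it reproduces: 6 + 6 + 3 + 3 + 10 = 28. It supplies the denominators and is not in dispute. The plan is descriptive, so there is no power calculation to check.

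**1. Does the laboratory plot show change?** Two constructed examples, with values in arbitrary units:

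- n = 3 (the size of Groups 3 and 4). Day 0: 20, 40, 90. Day 7, same participants in order: 90, 40, 20. Both days have median 40 and range 20 to 90. The changes are +70, 0 and −70, and one participant has risen 90/20 = 4.5-fold.
- n = 6 (the size of Groups 1 and 2). Day 0: 10, 20, 30, 40, 50, 60. Day 7: 60, 10, 20, 30, 40, 50. Both days have median 35 and range 10 to 60. The changes are +50 once and −10 five times, so the median change is −10.

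The same plot would appear if nobody had changed at all. Median and range of values therefore do not determine change from baseline.

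**2. Which draws does the plot use?** From the biochemistry and haematology rows in section 8:

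| Groups | Draws following a dose | Plotted | Share |
|---|---|---|---|
| 1 to 4 | days 2, 7, 28 | day 7 | 1 of 3 |
| 5, if the text means the prime only | days 2, 7, 28, 58, 63, 84 | day 7 | 1 of 6 |
| 5, if the text covers each dose | same | days 7 and 63 | 2 of 6 |

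The Group 5 draw on day 56 is taken at the boost visit. It is treated here as the pre-boost sample, as section 6.1 treats the vaccination visit as baseline, so it is not counted as following a dose.

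**3. What does one Group 5 row hide?** Suppose the row shows 2/10, that is 20% with an exact 95% interval of 2.5% to 55.6%. The entry is the same whether both events followed the prime, both followed the boost, or there was one of each.

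For the denominator, the SAP gives no figure for how many will be boosted; assume 8 to 10. With zero events the exact 95% upper limit is 1 − 0.025^(1/n):

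- n = 10: 1 − 0.025^(1/10) = 30.8%
- n = 9: 1 − 0.025^(1/9) = 33.6%
- n = 8: 1 − 0.025^(1/8) = 36.9%

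If only 8 receive the boost, using all 10 enrolled understates the upper limit for post-boost events by 36.9 − 30.8 = 6.1 percentage points. If all 10 are boosted the difference is nil.

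**4. Which adverse events have no column in Table 6?** Take a non-serious, expected event that begins between days 8 and 28 and does not meet the Grade 3 criterion. It is outside the 7-day columns by time, outside the 28-day column because it is expected, and outside the SAE column. It would appear only in the section 5.6 summary, which sets no 28-day window.

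The counting unit is also unsettled. The text of 6.1 counts participants ("The number with expected and unexpected AEs and all SAEs will be presented alongside"), while the table headings count signs, symptoms and events.

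**The case against.** The other side has several fair points.

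- **The range is plotted too.** It shows the extreme value at each time, and an identical plot needs an exact rearrangement of values, which is unlikely in practice. That limits how often the plot would mislead. It does not make it a display of change: a participant's rise that stays below the group's highest value does not move the upper end of the range.
- **Laboratory data have other routes.** Grade 3 laboratory events have their own holding rule in 3.2.3, day 7 bloods feed the safety reviews in 4.4, 4.6 and 4.7, and adverse events are summarised under 5.6. A reader might infer that collected safety data go unused or that individual abnormalities go unseen. The SAP does not support that. What is missing is a planned summary of change.
- **One Group 5 row answers the regimen question.** The objective covers the vaccines alone and in prime-boost, and Groups 1 to 4 address single vaccines. That justifies keeping the overall row, but not making it the only one. A reader might also infer that reactions could not be attributed to a vaccine. They could: diary cards are issued at both vaccination visits and events are ascertained after each. Only the table shell lacks the split.
- **The table is a sample, and its wording may be loose.** Expected and unexpected may stand for the solicited and unsolicited events of 3.2.3. If so, the 28-day point is one of terminology. A reader might infer that only unexpected events are counted at all. That is wrong: expected reactogenicity and SAEs have columns, and 5.6 carries no such restriction.

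**Conclusion.** The point holds, as a mismatch between listed measures and planned outputs that should be corrected before analysis.

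- Laboratory change from baseline has no specified output, and the planned plot covers 1 of 3 draws in Groups 1 to 4 and 1 or at most 2 of 6 in Group 5. This rests on the text of 3.2.2 and 6.1 and on reading the day 56 draw as pre-boost.
- Group 5's post-prime and post-boost events are merged over one enrolled denominator. The numerical effect depends on how many are boosted, which the SAP does not state.
- The 28-day gap is smaller and less certain, because 5.6 partly covers it and the labels may be loose.

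It would go too far to say that section 6.1 fails to deliver the primary safety measures as a whole, since 7-day reactogenicity and SAEs both have columns. The maximum tolerated dose and holding decisions rest on Grade 3 reactions and the rules in 3.2.3, not on these displays, and no sample size or error rate is affected.

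**What to change.** Three edits to section 6.1:

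1. **Laboratory measures.** Show each participant's change from the pre-dose value at every scheduled draw, as individual lines by group. Use day 0 as reference for post-prime draws and, in Group 5, the pre-boost sample from the day 56 visit for post-boost draws. The median and range plot can stay as a supplement.
2. **Adverse events to day 28.** Make the 28-day column of Table 6 count all adverse events, or all unsolicited ones beside solicited 7-day columns. State one counting unit for text and table; if both participants and events are wanted, label them separately.
3. **Group 5.** Add a post-prime row and a post-boost row, each with the number who received that vaccine as denominator, and keep the overall row for the regimen. End the post-prime row at each participant's actual boost: the visit has a window of ±7 days, so a fixed day 56 cut could put post-boost time in the wrong row.

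The cost is a few plots and table rows from data the schedule already collects. The analysis remains descriptive, consistent with section 6.3, and no visit, sample or clinical rule changes.
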